#### Windows for multiple assessments

In order to summarize weight, vital signs, ECGs, and laboratory tests collected over time (including unscheduled visits), the assessments will be time slotted. The following general rule will be applied in creating the assessment windows: If more than one assessment is done within the same time window, the assessment performed closest to the target date will be used. If 2 assessments within a time window are equidistant from the target date, then the earlier of the 2 assessments will be used. If there are multiple assessments on the same date, then the worst

Novartis	Confidential	Page 16 of 43
SAP Amendment 2		Study No. CAAA405A12302

case will be used. Data from all assessments (scheduled and unscheduled), including multiple assessments, will be listed.

Table 2-1	Time windows	
Time Window	Planned Visit Timing	Time Window Definition
On treatment		
Baseline (pre-treatment)	On or before Study Day 1*	Before Study Day 1, or on Study Day 1 but prior to [  F]CTT1057 injection
Day 1	Study Day 1	Date of [  F]CTT1057 injection
Day 15	Study Day 15	$14 - 17$ days after the date of $[^{18}F]CTT1057$ injection

\*Study Day 1 = the date of  $[^{18}F]$ CTT1057 injection

Electrocardiograms (ECGs) (for the PK subset) and vital signs will be assessed pre-injection, post-injection/ pre-imaging and post-imaging on Study Day 1. Their results will be presented by timepoint.

#### 2.2 Analysis sets

....

The Full Analysis Set (FAS) includes all enrolled participants.

The **Efficacy Analysis Set (EFF)** includes all enrolled participants who receive the dose of investigational treatment (i.e. [18F]CTT1057), have both an evaluable [18F]CTT1057 PET/CT scan and histopathology assessment, and have not received any prohibited systemic antineoplastic therapy before the completion of PET/CT and surgery.

The **Safety Set (SAF)** includes all participants who received the investigational treatment (i.e.  $[^{18}F]CTT1057$ ).

The **Pharmacokinetic analysis set (PAS)** includes all participants who provide at least one evaluable PK parameter. A profile is considered evaluable if all of the following conditions are satisfied: participant receives the investigational treatment (i.e. [F]CTT1057) and provides at least one primary PK parameter. The PAS will be used for all PK analyses.

Approximately 10 participants from the same site are expected to provide at least one evaluable PK parameter.

Note: Participants may be removed from the estimation of certain PK parameters on an individual basis depending on the number of available blood samples. Specific time points might be removed from the analysis set if technical issues with sample are reported (e.g. sampling issues, missing information) or if Lower Limit of Quantification (LLOQ) sample is observed between measurable concentrations. These participants and concentration data points will be identified at the time of analysis.

Novartis	Confidential	Page 17 of 43
SAP Amendment 2		Study No. CAAA405A12302

The number (%) of participants in each analysis set will be summarized and information about analysis sets for each participant will be displayed in a listing.

### 2.2.1 Subgroup of interest

The co-primary efficacy endpoints will be summarized by the following subgroups:

(a) PSA level at baseline (from central laboratory)

- $PSA \le 20 \text{ ng/mL}$
- PSA > 20 ng/mL

(b) Gleason Score

- Grade Group 1 Gleason score  $\leq 6$
- Grade Group 2 Gleason score 7 (or 3 + 4 = 7)
- Grade Group 3 Gleason score 7 (or 4 + 3 = 7)
- Grade Group 4 Gleason score 8
- Grade Group 5 Gleason score 9 or 10

(c) Number of pelvic lymph nodes (PLNs) dissected during the surgery

- PLNs < 12
- $PLNs \ge 12$

# 2.3 Patient disposition, demographics and other baseline characteristics

### 2.3.1 Patient disposition

Enrollment by country or subdivision and center will be summarized for all screened participants. The number (%) of screen failures and the reasons for screen failure will also be displayed. For participants screened more than once, the data from the last screening visit will be used in the summaries.

The following summaries will be provided (with % based on the total number of FAS participants unless otherwise specified):

- Number (%) of participants who were screened, and number (%) who were screened but not enrolled with the reasons for participants not enrolled (based on the 'Disposition' page and with % based on all screened participants)
  - Number (%) of participants who were not enrolled related to COVID-19 and primary relationships to COVID-19 (based on the 'Disposition' page and with % based on all screened participants)
- Number of participants (%) who were enrolled (i.e. FAS, based on the 'Subject ID' page)
- Number of participants (%) who completed study treatment phase (PET imaging completed)
- Number of participants (%) who were discontinued from study treatment phase and reason for discontinuation

 Number of participants (%) who were discontinued from study treatment phase related to COVID-19 and relationship to COVID-19

Novartis	Confidential	Page 18 of 43
SAP Amendment 2		Study No. CAAA405A12302

- Number of participants (%) who were dosed with [F]CTT1057 but not scanned and reason for not scanned
- Number of participants (%) who were not dosed with [F]CTT1057 and reason for not dosed

 $\circ~$  Number of participants (%) who were not dosed with [^{18}F]CTT1057 related to COVID-19 and relationship to COVID-19

- Number (%) of participants who completed the study (based on the 'Disposition' page)
- Number (%) of participants who discontinued the study and the reason for discontinuation (based on the 'Disposition' page)
  - Number (%) of participants who discontinued the study related to COVID-19 and primary relationships to COVID-19 (based on the 'Disposition' page)

#### Protocol deviations

The number (%) of participants in the FAS with any confirmed protocol deviation will be tabulated by deviation category (as specified in the study Data Handling Plan). All protocol deviations will be listed. For all important protocol deviations, the relationship to COVID-19 will also be captured.

#### 2.3.2 Demographics and other baseline characteristics

The FAS and EFF will be used for all baseline and demographic summaries and listings unless otherwise specified. Listings will be provided using the FAS.

#### Basic demographic and background data

All demographic and baseline disease characteristics data will be summarized and listed. Categorical data (e.g. Age groups: < 65 and  $\geq$  65 years, race, ethnicity, ECOG others as applicable) will be summarized by frequency counts and percentages; the number and percentage of participants with missing data will be provided. Continuous data (e.g. age, weight, height, body mass index (BMI), PSA level at screening from central laboratory) will be summarized by descriptive statistics (N, mean, median, 1st and 3rd quartile, standard deviation, minimum and maximum). BMI (kg/m^2) will be calculated as weight[kg] / (height[m^2]) using weight at Baseline.

#### Diagnosis and extent of cancer

Diagnosis and extent of cancer will be summarized and listed. This analysis will include the following: PSA level at time of initial diagnosis (ng/mL), primary tumor clinical stage (i.e. T2c or less, T3, T3a, T3b, T4 and Tx), biopsy predominant histology/cytology, percentage of each histological type/pattern, biopsy Gleason score (i.e.  $\leq 6$ , 7 (3+4), 7 (4+3), 8, and 9 or 10), time since initial diagnosis (in months). Note: biopsy Gleason score will be displayed along with the score details for each score combination in the table.

Derivation:

Time since initial diagnosis to PET scan (in months) = (date of PET scan – date of first prostate cancer diagnosis + 1) / 30.4375

#### **ECOG Performance Status**

ECOG performance status at baseline will be presented in a summary table and will be listed.

#### Medical history

Medical history and ongoing conditions, including cancer-related conditions and symptoms entered on eCRF will be summarized and listed. Separate summaries will be presented for ongoing and historical medical conditions. The summaries will be presented by primary system organ class (SOC), preferred term (PT). Medical history and current medical conditions will be coded using the Medical Dictionary for Regulatory Activities (MedDRA) terminology. The MedDRA version used for reporting will be specified in the CSR and as a footnote in the applicable tables/listings.

#### 2.4 Treatments (study treatment, rescue medication, concomitant therapies, compliance)

#### 2.4.1 Study treatment / compliance

The following exposure information of [F]CTT1057 as reported in the '[F]CTT1057 study treatment injection' page of the eCRF will be summarized (with % based on the total number of SAF participants unless otherwise specified ):

- Descriptive statistics of radioactivity dose administered (MBq) •
- Number (%) of participants who were dosed but with problems (i.e. extravasation) in • administration
- Number (%) of participants with dose administered outside the planned range (i.e. < 266٠ MBq or > 407 MBq)
- Time (in minutes) from injection to full-body PET imaging acquisition start time (based on the '[F]CTT1057 PET/CT Imaging - Local reads' page)
- Number (%) of participants with additional pelvic PET imaging acquisition, with time (in • minutes) from injection to additional pelvic PET imaging acquisition start time, if applicable (based on the '[F]CTT1057 PET/CT Imaging - Local reads' page)
- Time (in days) from full-body PET imaging acquisition start time to the date of surgery • (based on the '[F]CTT1057 PET/CT Imaging - Local reads' page and the 'Radical prostatectomy and ePLN dissection - Local histopathology assessment' page)

Participant level listings of doses administered or not, along with reasons if not administered will be produced using the FAS.

#### 2.4.2 Prior, concomitant and post therapies

#### **Prior anti-cancer therapy**

The number and percentage of participants who received any prior anti-neoplastic medications, prior anti-neoplastic radiotherapy or prior anti-neoplastic surgery will be summarized. Prior anti-neoplastic medications will be summarized by total number of regimens, setting (e.g. neoadjuvant, adjuvant, metastatic, etc.), and also by lowest ATC class and preferred term. Prior anti-neoplastic radiotherapies will be summarized by method (i.e. external beam vs. internal

Novartis	Confidential	Page 20 of 43
SAP Amendment 2		Study No. CAAA405A12302

beam) and setting (e.g. neo-adjuvant, adjuvant, metastatic, etc.). Prior anti-neoplastic surgeries will be summarized by procedure (i.e. radical prostatectomy vs. other) and residual disease (e.g. yes, no, etc.).

Separate listings will be produced for prior anti-neoplastic medications, radiotherapy, and surgery using the FAS.

Anti-neoplastic medications will be coded using the WHO Drug Dictionary (WHO-DD); antineoplastic surgery will be coded using MedDRA. Details regarding MedDRA and WHO-DD version will be included in the footnote in the tables/listings.

The above summary tables will be provided using the FAS and EFF.

#### Concomitant medications

Concomitant therapy is defined as all interventions (therapeutic treatments and procedures) other than the study treatment administered to a participant coinciding with the study treatment period. Concomitant therapy includes medications (other than study drugs) /therapies/procedures starting on or after the start date of study treatment or medications/therapies/procedures starting prior to the start date of study treatment and continuing after the start date of study treatment.

Concomitant medications will be coded using the World Health Organization (WHO) Drug Reference Listing (DRL) dictionary that employs the WHO Anatomical Therapeutic Chemical (ATC) classification system and summarized by lowest ATC class and preferred term using frequency counts and percentages. Surgical and medical procedures will be coded using MedDRA and summarized by SOC and preferred term. These summaries will include:

- 1. Medications/therapies/procedures starting on or after the start of study treatment but no later than 14 days after study treatment
- 2. Medications/therapies/procedures starting prior to start of study treatment and continuing after the start of study treatment.

The number of participants (%) who received diuretics (e.g. Furosemide) as concomitant medication on the day of PET/CT will also be summarized.

All concomitant therapies will be listed. Any concomitant therapies starting and ending prior to the start of study treatment or starting more than 14 days after the last date of study treatment will be flagged in the listing. The SAF will be used for all concomitant medication tables and listings.

### 2.5 Analysis supporting primary objective(s)

The primary objectives of the study are to evaluate patient-level sensitivity of [F]CTT1057and region-level specificity of [F]CTT1057.

#### 2.5.1 **Primary endpoint(s)**

The co-primary endpoints evaluated for participants in the EFF are the following:

**Patient-level Sensitivity** of  $[^{18}F]CTT1057$  PET imaging, defined as the proportion of participants that test positive on both  $[^{18}F]CTT1057$  and SoT (TP) among those that are SoT

Novartis
SAP Amendment 2

positive (TP + FN), considering PSMA positive participants are those who show at least one pathological [ $^{18}$ F]CTT1057 uptake either in the primary tumor (prostate region) and/or metastatic PLN region, with anatomically localized correspondence with the SoT. See Section 1.2.1 for Primary Estimand.

**Region-level Specificity** of [18F]CTT1057 PET imaging, defined as the proportion of PLN regions that test negative on both [ $^{18}$ F]CTT1057 and SoT (TN) among those PLN regions that test negative on the SoT (TN + FP), considering PSMA negative PLN regions are those which do not show any pathological [18F]CTT1057 uptake within the region. See Section 1.2.1 for Primary Estimand.

#### 2.5.2 Statistical hypothesis, model, and method of analysis

To address the co-primary efficacy objectives:

Patient-level sensitivity along with two-sided exact binomial 95% CIs will be calculated.

The lower bound of the 95% CI for patient-level sensitivity should be greater than 0.50 to attain the first co-primary endpoint.

**Region-level specificity** along with two-sided exact binomial 95% CIs will be calculated. Only pelvic lymph node regions will be used to calculate the specificity. The lower bound of the 95% CI for specificity should be greater than 0.70 for the study to attain the second co-primary endpoint.

An individual PET reader will be considered successful if he/she meets the predefined thresholds for both co-primary endpoints, and at least two of three readers should be successful for overall study positivity.

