## **4 Rationale**

### **4.1 Rationale for study design**

In this study, a single-dose of the investigational PET imaging radiopharmaceutical [ $^{18}\text{F}$ ]CTT1057 will be administered intravenously, in an open-label single-arm design.

The most commonly used measures for evaluating the diagnostic performance of a new imaging modality are sensitivity and specificity. Histopathology of the tumor samples is considered as the SoT to assess the diagnostic performance of PET tracers targeting PSMA ([Maurer et al 2016](#), [Woythal et al 2018](#), [Kuten et al 2020](#)). In PS patients, both the primary tumor and the metastatic lymph nodes (LN) are expressing PSMA, which is the target for [ $^{18}\text{F}$ ]CTT1057 binding. Within a period of up to 6 weeks after completion of the [ $^{18}\text{F}$ ]CTT1057 PET/CT scan, patients will undergo surgery as per their standard of care treatment plan, consisting of RP and ePLND, as per the European Association of Urology (EAU) guidelines for Prostate Cancer 2020 (refer to [Section 16.1](#)).

In addition to the prostate dissection, a minimum of 12 PLN per patient will be dissected in order to have enough numbers of PLN in total for the calculation of the co-primary endpoints and the diagnostic performance yielding secondary endpoints.

Local pathologists with experience in PCa who will be blinded to the [F]CTT1057 PET/CT results will then assess the tissue specimens as per SoC. For the anatomical correspondence with PET/CT images, a sextant template will be used for the prostate (Kuten et al 2020). For the PLN, an anatomical side approach left/right will be used, since the borders of dissection are not usually very clear neither for the surgeon nor for the pathologist.

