### 12.4.1 Definition of primary endpoint(s)/estimand(s)

The co-primary endpoints of the study are patient-level sensitivity and region-level specificity.

- Patient-level sensitivity is defined as the proportion of PSMA TP patients among PSMA TP patients and PSMA FN patients.
  - PSMA TP patients are those who show at least one pathological [F]CTT1057 uptake either in the primary tumor and/or metastatic PLNs with anatomically localized correspondence with the SoT.
  - PSMA FN patients are those who do not show any pathological [F]CTT1057 uptake either in the primary tumor or metastatic PLNs but will be confirmed having primary tumor or metastatic PLNs with the SoT.
- Region-level specificity is defined as the proportion of PSMA TN PLN regions among PSMA TN PLN regions and PSMA FP PLN regions.
  - PSMA TN PLN regions are regions that test negative for PLN on [F]CTT1057 and confirmed negative on the SoT.
  - PSMA FP PLN regions are regions that test positive for PLN on [F]CTT1057 but verified negative on the SoT.

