A large variability in sensitivity of PSMA-PET in the primary staging setting has been reported. Two recent systematic reviews of [Ga]PSMA PET /CT diagnostic accuracy focused on the PS population using pathology as SoT, sensitivity of 33–99% across studies has been reported (Corfield et al 2018), as well as pooled sensitivity and specificity ranges of 23-100% and 67-100% respectively (Petersen and Zacho 2020). Recent preliminary data on the diagnostic efficacy of F-18-rhPSMA-7.3 PET imaging in PS patients compared to histopathology (n=56) reported a 95% CI low bound patient level sensitivity of 54.4% (81.3 (95% CI-54.4-96.0) (Maurer et al 2020). CT and MRI are the standard of care imaging procedures for measuring tumors at baseline and lesions selected for response assessment as per RECIST criteria 1.1 (Eisenhauer et al 2009). A meta-analysis on the diagnostic accuracy of CT and MRI in the staging of pelvic lymph nodes in patients with PCa reported a pooled sensitivity of 0.42 (95% CI 0.26-0.56) for CT, and of 0.39 (95% CI 0.22-0.56) for MRI (Hövels et al 2008). A study evaluating the diagnostic value of [Ga]PSMA PET versus CT and MRI for lymph node staging in 130 consecutive patients who got RP and PLN dissection after PET/Magnetic Resonance (MR) (n=95) and PET/CT (n=35) and who had tumor specimens available for reanalysis to correlate with PET reported a sensitivity of 43.9% (95% CI 28.5-60.3) and 85.4% specificity (95% CI 76.3-92.0) for morphological imaging alone (CT and MRI) (Maurer et al 2016).

Taking all the above into consideration, an overall patient-level sensitivity of 50% and a region level specificity of 70% will be considered as unacceptably low. Hence, the sample size calculation will be performed based on the null and alternative hypotheses as follows.

- Patient-level sensitivity

For patient-level sensitivity, the null hypothesis H0: patient-level sensitivity p0 = 0.50 will be tested against the alternative hypothesis H1: p1>0.50, assuming a sensitivity of 0.63 under the alternative hypothesis, approximately 156 patients with primary tumor and/or metastatic lymph nodes would achieve 90% statistical power to detect a change in sensitivity of 0.13 using a one-sided binomial test at a target significance level of 2.5%. Taking into account 20% dropout rate, 195 patients can ensure the 90% statistical power.

- Region-level specificity

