## 2.6.1 Secondary endpoint(s)

Secondary endpoints are defined for the EFF unless otherwise specified with details given as follows:

**Patient-level specificity** is defined as the proportion of TN participants among those who are TN or FP.

**Patient-level positive predictive value** is defined as the proportion of TP participants among those who are TP or FP.

**Patient-level negative predictive value** is defined as the proportion of TN participants among those who are TN or FN.

**Patient-level accuracy** is defined as the proportion of TP and TN participants among all participants in EFF (regardless of TP, TN, FP, FN)

where TP, TN, FP, FN participants are defined as follows:

- PSMA TP participants are those who show at least one pathological [F]CTT1057 uptake either in the primary tumor and/or metastatic PLNs with anatomically localized correspondence with the SoT, regardless of co-existing FP lesions in those two regions.
- PSMA TN participants are those who do not show any pathological [F]CTT1057 uptake neither in the primary tumor nor metastatic PLNs and will be confirmed NOT having primary tumor nor metastatic PLNs with the SoT.
- PSMA FP participants are those who are not TP and show at least one pathological [F]CTT1057 uptake either in the primary tumor and/or metastatic PLNs but will be verified NOT having primary tumor nor metastatic PLNs with the SoT or none of the lesions is correctly localized in anatomical location by the SoT.
- PSMA FN participants are those who do not show any pathological [F]CTT1057 uptake neither in the primary tumor nor metastatic PLNs but will be confirmed having primary tumor or metastatic PLNs with the SoT.

Number of TP, TN, FP, FN participants will be presented and used to calculate the diagnostic performance parameters.

Two-sided exact binomial 95% CIs for diagnostic performance parameters will be calculated.

**Region-level sensitivity** is defined as the proportion of TP PLN regions among those that are TP or FN.

**Region-level sensitivity** will also be presented, excluding PLNs showing metastasis < 2 mm (micro-metastasis).

**Region-level positive predictive value** is defined as the proportion of TP PLN regions among those that are TP or FP.

Novartis	Confidential	Page 24 of 43
SAP Amendment 2		Study No. CAAA405A12302

**Region-level negative predictive value** is defined as the proportion of TN PLN regions among those that are TN or FN.

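### Neither the prostate nor the pelvic nodes has its own sensitivity-specificity pair in the success rule, so missed nodes and over-called prostate sextants carry no penalty

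*SAP*

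**What the plan says.** - **Sensitivity.** SAP 2.5.1 counts a participant as positive with at least one pathological uptake "either in the primary tumor (prostate region) and/or" a metastatic PLN region, provided that it corresponds anatomically with histopathology, the standard of truth (SoT). The denominator is the SoT-positive participants, written as TP + FN. Protocol 12.4.1 has the same at-least-one rule: "PSMA TP patients are those who show at least one pathological" uptake in either site.
- **Extra foci.** SAP 2.6.1 keeps such a man a TP "regardless of co-existing FP lesions in those two regions". The same list puts a PET-positive man with no correctly localised lesion under FP, and reserves FN for men with no pathological uptake in either site.
- **Specificity.** SAP 2.5.2: "Only pelvic lymph node regions will be used to calculate the specificity".
- **Success rule.** SAP 2.5.2: "The lower bound of the 95% CI for patient-level sensitivity should be greater than 0.50 to attain the first co-primary endpoint", and "The lower bound of the 95% CI for specificity should be greater than 0.70 for the study to attain the second co-primary endpoint". A reader must meet both, and two of the three readers must succeed.
- **Matching.** Protocol 4.1: "For the anatomical correspondence with PET/CT images, a sextant template will be used for the prostate". The PLN are matched by side, left or right.
- **Rationale.** Protocol 12.8.1 states that "an overall patient-level sensitivity of 50% and a region level specificity of 70% will be considered as unacceptably low". It makes region-level sensitivity secondary because about 520 patients would be needed to yield 156 positive PLN.

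**The concern.** The primary clinical question (Protocol 2.1, SAP 1.2.1) is whether the tracer can detect and localise disease. Two kinds of error do not touch the success rule. A missed node costs nothing in a man whose prostate focus matches. A false-positive sextant costs nothing because the man stays TP and specificity ignores the prostate. Every participant has biopsy-proven cancer (Protocol 5.1), and at the plan's 30% nodal prevalence about 70% of men can be TP only through the prostate. The composite is therefore driven by the prostate.

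The secondary endpoints close only part of the gap. PLN-region sensitivity is planned but has no threshold. Over-calling inside the prostate is measured by no analysis in the public text. Patient-level specificity needs men without tumour on the SoT, and this population will supply almost none.

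At stake is what a positive result may be said to show. A separate defect is that two SAP sections disagree on who is in the sensitivity denominator.

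**Working it through.** **Inputs.** 156 evaluable of 195 enrolled, 20% dropout, one-sided 2.5%, sensitivity 0.63 against 0.50, specificity 0.85 against 0.70, nodal prevalence 30% (Protocol 12.8.1, SAP 3.1). Published nodal prevalence range 4-58% (Protocol 12.8.1). Exact (Clopper-Pearson) intervals (SAP 5.4.1). Assumptions: all 156 men have tumour on the SoT, and there is one PLN region per man.

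**1. The plan's own figures reproduce.**
- Sensitivity, n = 156: the smallest count with an exact lower limit above 0.50 is 91. Attained alpha is 0.0225 and power 0.901. 156/0.8 = 195.
- Specificity: 123 × 0.70 = 86 negative men, smallest passing count 69, power 0.914. 123/0.8 = 154.
- Nodal sensitivity: 156/0.30 = 520.

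**2. Stress-test reader: all six sextants positive, every PLN region negative.** For x = n the exact lower limit is 0.025^(1/n).
- Sensitivity 156/156: 0.025^(1/156) = 0.977, above 0.50.
- Specificity, 156 × 0.70 = 109 negative men: 0.025^(1/109) = 0.967, above 0.70. At 4% prevalence it is 150/150, lower limit 0.976; at 58%, 66/66, lower limit 0.946. With two regions in each node-negative man, 218/218 gives 0.983.
- Nodal sensitivity 0/47: upper limit 1 - 0.025^(1/47) = 0.075.

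Both co-primaries pass at any documented prevalence, with no node found.

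**3. How much the anatomical match protects.** If k of 6 sextants hold tumour and m are marked at random, the match probability is 1 - C(6-k, m)/C(6, m). With mislocalised men kept in the denominator, passing needs at least 91 matches in 156. The documents give no figure for k, so a range is shown.

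| Sextants with tumour (assumed) | One marked: match, P(pass) | Two marked: match, P(pass) |
|---|---|---|
| 1 of 6 | 0.17, 0.000 | 0.33, 0.000 |
| 2 of 6 | 0.33, 0.000 | 0.60, 0.695 |
| 3 of 6 | 0.50, 0.023 | 0.80, about 1.0 |
| 4 of 6 | 0.67, 0.988 | not needed |

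The match requirement blocks sparse guessing unless tumour is extensive. It does not block over-calling: each extra sextant raises the chance of a match and costs nothing.

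**4. The denominator conflict.** Under SAP 2.6.1 a mislocalised SoT-positive man is FP, hence outside TP + FN. Under the description in SAP 2.5.1 he is SoT-positive and belongs in the denominator. An illustrative split of 156 men into 80 TP, 40 FN and 36 mislocalised gives:
- SAP 2.6.1: 80/120 = 0.667, lower limit 0.575, pass.
- All SoT-positive men: 80/156 = 0.513, lower limit 0.432, fail.

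In the extreme, a reader who marks something in every prostate has no FN, so sensitivity is TP/TP = 100% whatever the match rate. Six matches then suffice (lower limit 0.541); five do not (0.478).

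**5. PLN index J = sensitivity + specificity - 1, Wald interval.** With 47 positive and 109 negative men, sensitivity 0.50 and specificity 0.85: J = 0.35, SE = √(0.25/47 + 0.1275/109) = 0.081, lower limit 0.19. With the CT/MRI figures cited in Protocol 12.8.1 (43.9% and 85.4%): J = 0.29, lower limit 0.14. At 4% prevalence (6 positive, 150 negative) J = 0.35 has a lower limit of -0.05. So J above zero would not separate the tracer from conventional imaging, and its precision depends on prevalence.

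**The case against.** The nodal gap is a disclosed and reasoned choice. As a third co-primary at 0.63 against 0.50, nodal sensitivity would rest on about 47 men, need 31 successes and have 40% power. Full power needs 520 evaluable men, or 520/0.8 = 650 enrolled. PLN sensitivity (with and without micro-metastases), predictive values and accuracy are already planned with exact intervals, and each reader is compared separately with the SoT, so the stress-test reader would be exposed as 0/47. Central readers are blinded and apply uptake criteria (Protocol 4.1), so that reader is a logical test and not a forecast. All of this stands. It is why the co-primaries should not change. It does not define what success means, measure over-calling in the prostate, or settle the denominator.

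Someone might also draw stronger conclusions that the documents do not support:
- That the two endpoints test different organs. They overlap on the PLN.
- That calling every prostate positive is enough. At least one location must match.
- That chance localisation generally passes. One random sextant fails in nearly every trial when up to 3 of 6 are involved.
- That success is meant to show superiority to CT or MRI nodal staging. Nodal CT/MRI figures help to justify the 0.50 floor, but no objective or test makes that claim.

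**Conclusion.** The point holds in a limited form and merits a SHOULD-level change; it does not invalidate the design. The success rule cannot tell good nodal detection from none, and it does not penalise over-calling in the prostate. The stress-test reader clears both thresholds by a wide margin (0.977 against 0.50; 0.967 against 0.70) with 0/47 nodes found. Localisation is tested, but only as at least one match. The disagreement between SAP 2.5.1 and 2.6.1 is a concrete inconsistency that can decide the first co-primary if mislocalised men are numerous; the 36 used above is an illustration. The counts rest on 156 SoT-positive men and one PLN region per man, and the 47/109 split on 30% prevalence. The stress-test result holds across 4-58%. The guessing probabilities depend on an assumed number of involved sextants.

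**What to change.** Keep both co-primaries and both thresholds. Before database lock:

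1. In SAP 2.6.1 add, per reader, prostate sextant-level sensitivity and specificity with confidence intervals clustered by man, using the template already specified for matching.
2. Present the planned PLN-region sensitivity beside PLN-region specificity for each reader, with J and its 95% CI. Label J as descriptive and not as evidence of being better than CT or MRI.
3. State in SAP 2.5.2 that success means cancer detected in the prostate and/or PLN, with PLN specificity above 0.70, and that it does not by itself show nodal detection.
4. Align SAP 2.5.1 and 2.6.1: an SoT-positive man with no correctly localised lesion stays in the sensitivity denominator as a failure.

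The cost is SAP wording and two extra tables per reader, with no new patients, reads or procedures. Pathology location by template is already captured (Protocol 8.3.2); that the central read records sextants is assumed, since the matching requires it. The downside is a narrower success claim and possibly a lower sensitivity figure.
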